## 1.0 Background

**Obesity and obesity-related complications are leading causes of morbidity and mortality among Veterans**. Obese individuals experience a markedly increased risk of cardiovascular and metabolic ("cardiometabolic") diseases—including diabetes, hypertension, and coronary artery disease. The rising prevalence of these problems despite current therapies supports that obesity is a multifactorial disease and highlights the need for novel approaches to treat obesity-related cardiometabolic dysfunction.

**Evidence from genetic studies in animals and humans indicate that the natriuretic peptide (NP) system may protect against cardiometabolic risk.** The NPs are cardiac derived hormones, classically recognized for their role in the regulation of blood pressure and volume status. In recent years, animals studies and human genetic investigation have demonstrated that higher genetically-determined NP levels protect against development of hypertension, obesity, Type 2 diabetes, and metabolic syndrome. Further, administration of B-type natriuretic peptide (BNP) to wild-type mice leads to increased thermogenic gene expression in brown as well as white adipose depots, increased energy expenditure, and reduced fat accumulation. The increase in thermogenic gene expression in white adipose tissue reflects the development of "brown-like" or "beige" adipose tissue (a process referred to as "beiging"). Brown and beige adipose tissue increase energy expenditure by dissipating energy as heat (thermogenesis) through the actions of uncoupling protein 1 (UCP1). Promoting the development of a beige adipose phenotype could potentially lead to increases in energy expenditure, promote weight loss, and improve insulin sensitivity in obesity.

NP levels are lower in obese compared with lean individuals, and in black compared with white individuals, in human epidemiologic investigations. This suggests that low circulating NP levels may reflect a relative NP deficiency in obese and black individuals. As the NP system appears to protect against cardiometabolic risk, a relative NP deficiency could contribute to adverse cardiometabolic outcomes observed in obese and black individuals. Whether a relative NP deficiency in these groups is associated with reduced thermogenic gene expression and lower energy expenditure is not well understood.

#### 2.0 Rationale and Specific Aims

NP levels differ by obesity status and race in epidemiologic studies, and NPs appear to promote "beiging" of adipose tissue in animals. However, whether gene expression of beige adipose tissue differs by obesity status and race has not been established in humans. Human mechanistic studies investigating the relationships of beige adipose tissue markers with obesity status, race, and the natriuretic peptide system are limited. We propose an innovative physiologic study in which we will quantify adipose tissue gene expression and energy expenditure in states of relative NP deficiency in humans, namely in obese and black individuals. Our overarching postulate is that obese and black individuals have NP deficiencies that contribute to less beige adipose tissue and lower energy expenditure. Thus, we propose the following aims:

# Aim 1: Determine whether beige adipose tissue markers differ between obese and lean individuals.

We plan to enroll and conduct subcutaneous adipose biopsies on approximately 155 adult participants (aged 18-55 years; approximately 50 lean and 105 obese participants). We will quantify expression of genes indicative of "beiging" in subcutaneous adipose tissue biopsies and determine whether gene expression differs based on obesity status. In a secondary analysis, we will determine whether these beige adipose tissue markers differ by race.

Aim 2: Determine whether beige adipose tissue markers and energy expenditure are associated with natriuretic peptide receptor expression in adipose tissue and circulating natriuretic peptide levels. We will examine these associations in approximately 155 adult participants, as described in Aim 1.

## **Secondary Aims:**

- -Determine whether adipose tissue gene expression profiles suggestive of beiging differ by race.
- -Determine whether obesity-related differences in beige fat are attributable to differences in NP markers.
- -Examine associations of adipose tissue phenotypes with cardiometabolic parameters.

#### 3.0 Animal Studies and Previous Human Studies

#### The natriuretic peptide (NP) system and metabolism

**The NP system is classically known for its role regulating blood pressure and volume status**. In response to increased cardiac wall stress, the heart secretes atrial natriuretic peptide (ANP) and BNP, which both cause natriuresis, vasodilation, and inhibition of the renin-angiotensin-aldosterone system. Thus, the biologic actions of the NPs serve to reduce blood pressure. Both ANP and BNP bind to their target receptor, NPR-A, and are cleared by the clearance receptor, NPR-C.¹ NP receptors are widely present throughout the cardiovascular system, as well as in adipose tissue, skeletal muscle, liver, brain, and gut.

Although the NP system is classically known for its role in blood pressure regulation, recent studies have shown that NPs have important metabolic actions as well. Administration of NPs stimulate lipolysis in animals and humans.  Transgenic mice that overexpress BNP are protected against weight gain, visceral fat accumulation, and insulin resistance induced by high-fat diets.  Moreover, Bordiccia et al. demonstrated in wild-type mice that BNP administration over 7 days significantly increases energy expenditure and oxygen consumption.  The increases in energy expenditure and oxygen consumption appear to be mediated by increased expression of thermogenic genes (including UCP1) in brown adipose tissue, as well as white adipose tissue.  The increase in thermogenic gene expression in white adipose tissue reflects the development of beige fat.

**The NP system may protect against cardiometabolic risk.** In humans, a common genetic variant resulting in ~10-20% higher NP concentrations (still within the physiologic range) is associated with lower prevalence of hypertension (by 15%), obesity (by 46%), and metabolic syndrome (by 42%), and a lower risk of developing Type 2 diabetes (by 12%). Moreover, this genetic variant that causes higher NP levels is associated with favorable cardiovascular biomarkers and a lower prevalence of myocardial infarction. Conversely, humans with a genetic variant leading to lower NP levels exhibit higher risk of hypertension, future T2DM, and evidence of adverse cardiac remodeling. These data strongly suggest that the NP system may protect against cardiometabolic risk.

Obese and black individuals have low circulating NP levels, which appears to reflect a relative "NP deficiency." Multiple large cohort studies have demonstrated that NP levels are lower in obese compared with lean individuals, and in black compared with white individuals. Obese and black individuals have a propensity toward hypertension, which would be expected to cause higher circulating NP concentrations. Thus, the lower NP concentrations in obese and black individuals are physiologically inappropriate and likely reflect a relative NP deficiency. As the NP system appears to protect against cardiometabolic risk, a relative NP deficiency could raise susceptibility to the adverse cardiometabolic outcomes observed in obese and black individuals. The reasons for the low NP levels in obese and black individuals are not entirely known. One proposed mechanism for the low NP concentrations in obesity is enhanced NP clearance in adipose tissue. Obese individuals have been found to have higher expression of the NP clearance receptor in adipose tissue compared with lean individuals. 15 Despite these associations, thermogenic gene expression in adipose tissue and whole body energy expenditure in these relatively NP deficient groups are not well characterized and understood.

# 4.0 Inclusion/Exclusion Criteria

We will enroll and conduct subcutaneous adipose biopsies on approximately 155 participants (approximately 50 lean subjects (18.5≤BMI<25 kg/m²) and approximately 105 obese subjects (BMI≥30 kg/m²)). Full eligibility criteria are listed below.

#### **Inclusion Criteria:**

- Men and women ages 18-55 years
- Body Mass Index (BMI) ≥18.5 and <25 kg/m² (lean), or BMI ≥30 kg/m² (obese)

#### Exclusion Criteria:

- Significant pulmonary, liver, or renal disease
- Heart failure (any type), unstable coronary artery disease currently, or history of significant cardiac event or stroke within 12 months
- Diabetes Mellitus (Types 1 and 2)
- Thyroid dysfunction

- Active malignancy
- Chronic inflammatory diseases, such as inflammatory bowel disease, hepatitis, rheumatoid arthritis
- Current use of medications likely to affect energy homeostasis, including amphetamines and beta blockers, and significant use of systemic glucocorticoids
- Currently pregnant or breastfeeding, or unwilling to avoid becoming pregnant or breastfeeding during study duration
- Significant claustrophobia that would prevent the use of the metabolic cart as part of the study protocol
- Hemoglobin A1c (HbA1c) ≥6.5%
- Liver Function Tests (LFTs) elevated >3x upper limit of normal
- Estimated Glomerular Filtration Rate (eGFR) <40 ml/min

# 5.0 Enrollment/Randomization

Recruitment will take place at Tennessee Valley Healthcare System (TVHS) outpatient clinics, community-based outpatient clinics, veteran centers, veteran service organizations, Fort Campbell, and Vanderbilt University Medical Center (VUMC). All patients coming for outpatient services at TVHS may be considered. We will place IRB approved flyers and brochures in target clinics, veteran centers, Fort Campbell, and community boards (electronic and physical) with basic study information and study team contact information for potential subjects to signal potential interest. Working with the VA Public Affairs office, we will utilize their advertisement services such as waiting lobby TV advertisements, VA web homepage announcements, newspaper, and email distribution lists to veterans. A link may also be posted on My HealtheVet. We will also screen medical records in CPRS system (including data linked to CPRS through JLV and VISTA). VA subjects, once identified through the CPRS system, will be sent recruitment letters about participation in the study. The recruitment letters may be followed by a phone call to the participant. Study personnel may also approach possible study participants in clinic once permission is received by that subject's provider. Providers and clinic teams members within the VA or non-VA medical centers may also send referrals to the study team. Subjects may also be recruited using My HealthEVet and the VINCI system. Subjects may also be recruited via the Vanderbilt Broadcast email system. ([contact]). ResearchMatch.org may be utilized as a recruitment tool for this protocol. ResearchMatch.org is a national electronic, webbased recruitment tool that was created through the Clinical & Translational Science Awards Consortium in 2009 and is maintained at Vanderbilt University as an IRBapproved data repository. Study personnel may also use a VA-issued phone to communicate with recruited subjects (including phone calls and text messages for appointment reminders and logistical information). Text messages will not include any patient identifiers.

Due to recruitment setbacks related to COVID-19, some samples and data previously collected from another study, Cardiovascular Effects of GLP-1 Receptor Activation (P.I., Dr. [name] (Vanderbilt University Medical Center (VUMC) IRB# 170213, ClinicalTrials.gov Identifier: NCT03101930) will be included to help meet our enrollment goals for the obese subject population. In this prior study (VUMC IRB# 170213), obese individuals underwent the same study procedures that we are performing in the present study as outlined below (subcutaneous adipose tissue biopsy, indirect calorimetry, DXA body composition scan), and thus the samples/data have already been collected. These samples were of similar inclusion criteria as the currently recruiting study, with the minor adjustment of age criteria of up to 65 years of age. For the prior study (VUMC IRB#170213), subjects signed a consent form which indicated their consent for their samples/data to be used for future research. Samples provided from this study will be de-identified for our use. There are approximately 122 obese individuals from this prior study with available baseline samples/data relevant to any of our endpoints, of whom approximately 80 individuals have adipose biopsy data (our primary endpoint). The inclusion of these samples will enable us to analyze baseline data for approximately 105 obese subjects with adipose biopsy data (primary endpoint) (from the subjects that we are able to personally recruit, as well as the previously collected samples/data from the prior study).

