#### 10.0 Statistical Considerations

Sample size justification: A total of 100 subjects will provide 80% power to detect a minimum difference between lean and obese groups of 0.7 units of UCP1 mRNA expression normalized for housekeeping gene mRNA gene expression (primary analysis). This represents a metabolically meaningful difference of approximately 0.45 standard deviations between lean and obese groups. These calculations are based on a Type 1 error rate of 0.05, and interindividual variations in UCP1 gene expression reported in prior studies. Since there is only 1 main study visit, dropouts should not be an issue in this study. However, there is a low likelihood that some adipose tissue samples may be inadequate quantity or quality. Even if some adipose tissue samples are of insufficient quantity or quality, a sample size of 80 would still provide 80% power to detect a minimum difference between groups of 0.75 units in UCP1 normalized mRNA expression, which represents a metabolically meaningful difference of approximately 0.48 standard deviations between lean and obese groups.

Of note, the above sample size calculation was based on the original enrollment goal of 100 subjects. Now that we have the benefit of including some samples from a previously completed study, our statistical power to answer our scientific questions will be improved.

Statistical Analysis: The primary analysis will determine whether adipose tissue gene expression of UCP1 differs between lean and obese individuals. To assess this, we will use multivariable linear regression, with UCP1 gene expression as the outcome variable, and BMI as the independent variable. The multivariable linear regression will be adjusted for covariates that may impact markers of beige adipose tissue, including age and sex. The null hypothesis is that UCP1 gene expression will not differ based on BMI. Secondary analyses include whether UCP1 gene expression differs by race and whether expression of additional "beiging" markers differ by obesity status. Like the primary analysis, the secondary analyses are analyzing a continuous outcome variable. Thus, the statistical approach for the secondary analyses will be similar to that described for the primary analysis.

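### About 80 of some 105 obese biopsies, and by inference no lean ones, come from an earlier study, yet the primary BMI model states no study-source term or sensitivity analysis

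*Combined protocol and SAP*

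**What the plan says.** Section 5.0 explains that samples and data from an earlier study of GLP-1 receptor activation "will be included to help meet our enrollment goals for the obese subject population". About 122 obese people from that study have some relevant baseline data, "of whom approximately 80 individuals have adipose biopsy data (our primary endpoint". With new recruits, this lets the team "analyze baseline data for approximately 105 obese subjects with adipose biopsy data (primary endpoint". Aim 1 (Section 2.0) gives the whole sample as "approximately 155 adult participants (aged 18-55 years; approximately 50 lean and 105 obese participants". No lean participant is described as coming from the earlier study. That none does is an inference, though a natural one.

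On comparability, Section 5.0 says that "obese individuals underwent the same study procedures that we are performing in the present study" and names biopsy, calorimetry and DXA. It calls the inclusion criteria similar, "with the minor adjustment of age criteria of up to 65 years of age". Section 4.0 lists only "Men and women ages 18-55 years".

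Section 10.0 sets the primary model, with "UCP1 gene expression as the outcome variable, and BMI as the independent variable", adjusted for covariates of which age and sex are named. The borrowed samples appear there only as a gain in power. No section states a source term, a comparison of the two sources, or a sensitivity analysis for pooling.

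**The concern.** Pooling one exposure group mostly from another study ties study source to the exposure. Anything that makes measured UCP1 differ between the studies, and that age and sex do not capture, then looks in part like a BMI effect. Depending on its direction, it could create an association in the primary endpoint or hide a real one. Section 10.0 expresses its target as a lean-obese difference of about 0.45 SD, so even a modest source shift would be sizeable against it. The roughly 25 obese participants recruited alongside the lean group make a source-adjusted estimate possible from data already held, but the plan does not commit to one. Because the covariate list is open, the choice could also be made after the data are seen.

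**Working it through.** **The plan's own figure.** Section 10.0 states 80% power at 0.45 SD with 100 participants. With a 50/50 split (assumed), two-sided 5%, power = Φ(0.45/√(1/50+1/50) − 1.96) = Φ(2.25 − 1.96) = 61%. So 80% is not reproduced by this formula. That is a separate matter: only the 0.45 SD is used here, as a yardstick. The plan gives no figure for the gain from pooling.

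**Counts (Sections 2.0 and 5.0, all approximate).** Lean 50, obese 105, total 155. Prior-study obese 80; concurrent obese 105 − 80 = 25. Prior share of the obese group 80/105 = 76%; of the lean group 0/50 (inferred); overall 80/155 = 52%.

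**Link between exposure and source.** For lean/obese, the correlation is (80×50 − 25×0)/√(105×50×80×75) = 4000/5612 = 0.71. For continuous BMI it is about 0.63-0.65 under the distributions below.

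**Effect of a source shift.** Simulation, 4,000 runs per cell, no true BMI effect, constant additive shift in prior-study samples. Everything in this list is assumed, because the documents give no such data:
- lean BMI normal, mean 22.5, SD 1.6, truncated to 18.5-25;
- obese BMI normal, mean 36, 37 or 38 with SD 4, 5 or 6, truncated to 30-60, the same in both sources;
- age uniform 18-65 in the prior study, 18-55 otherwise;
- 50% of each sex.

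Both models below adjust for age and sex. Ranges cover the three BMI settings and repeat runs.

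| Assumed shift (SD) | Bias at the mean lean-obese BMI gap, continuous BMI (SD) | Type I error, continuous BMI | Type I error, lean/obese |
|---|---|---|---|
| 0.1 | 0.06 | 6-7% | 6-8% |
| 0.2 | 0.11-0.13 | 11-13% | 13-14% |
| 0.3 | 0.17-0.19 | 19-21% | 23-25% |
| 0.5 | 0.28-0.31 | 44-50% | 53-56% |

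At 0.3 SD the bias is 0.17/0.45 to 0.19/0.45, or 38-42% of the plan's yardstick. With a source term, type I error returns to about 5% in either model if the shift is constant. If a mean 0.3 SD shift grows with BMI, the source-adjusted BMI model still rejects in about 12% of runs (39% without the term).

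**Masking.** A true linear BMI effect with 77-81% pooled power keeps 48-56%, 33-40% and 11-16% against opposite shifts of 0.2, 0.3 and 0.5 SD. Source-adjusted power is 53-62% throughout, again if the effect is linear.

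**Price of adjustment.** For lean/obese with a source term, the contrast rests on 50 lean against 25 concurrent obese: the standard error grows by √(1/50+1/25)/√(1/50+1/105) = 0.245/0.172 = 1.43. The effect detectable with 80% power is about 0.70 SD, against 0.49 SD pooled. For linear BMI it is 0.55-0.59 against 0.43-0.45 SD.

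**What the within-obese comparison can show.** 80 against 25: SE = √(1/80+1/25) = 0.229 SD. Adjusted for age, sex and BMI, the 95% half-width is about 0.47 SD, and power at a 0.3 SD shift is about 24%.

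**Linearity.** Nobody with BMI from 25 to under 30 is enrolled. If UCP1 steps by 0.45 SD at obesity and there is no source effect, the BMI-plus-source model gives a spurious source coefficient of about 0.09-0.11 SD. The BMI estimate at the mean gap falls from 0.34-0.37 to 0.28-0.31 SD, and power from about 60-65% to 29-34%.

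**The case against.** The strongest reply is that no source effect is documented and that the documents lean towards comparability. Section 5.0 claims the same procedures, similar criteria and baseline data only. Section 6.0 places present-study visits at the Vanderbilt Clinical Research Center, and the earlier study was a Vanderbilt University Medical Center study. Section 5.0 also lists that centre as a recruitment site. UCP1 is normalised to a housekeeping gene. Age and sex are in the model, so only a residual difference matters, and the open covariate list does not forbid a source term. All of this stands. It lowers the likelihood of a large shift but does not replace a check: the list of shared procedures does not mention the UCP1 assay, and where the prior biopsies were taken is not stated.

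A reader might infer three stronger things that the documents do not support.
- **The primary result is biased.** Every shift above is hypothetical.
- **The two sources were assayed in separate batches or handled differently.** The documents do not say. Samples as well as data are to be supplied, so joint assay is possible, and the two tissue routes in Section 6.0 are both allowed within the present study.
- **Error rates of 26% and 60% at 0.3 and 0.5 SD.** These come from a two-group formula without age and sex, which is not the planned model.

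A further fair objection is that the remedy has its own weakness, because a BMI-plus-source model leans on linearity. That also stands and shapes the fix.

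On age, the extension to 65 is disclosed, and the Section 4.0 criterion can be read as applying to new recruits. What remains is the Aim 1 wording.

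**Conclusion.** The point holds as possible, unchecked confounding of the primary exposure by study source; it should be fixed. The structure is firm: 76% of the obese group and, by inference, none of the lean group come from the earlier study, with no source analysis stated. The size is conditional. It rests on assumed BMI and age distributions and on shifts that the documents neither report nor rule out. A constant shift of 0.1 SD would matter little; one of 0.3 SD would raise type I error to roughly 19-25%, depending on how obesity is coded. Calling the pooled analysis invalid would go beyond the documents. The age mismatch between Aim 1 and Section 5.0 is a smaller matter of wording.

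**What to change.** In Section 10.0, keep the pooled model as primary and add:

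1. A pre-specified sensitivity analysis: the same model (BMI, age, sex) plus a study-source term. Report the BMI estimates with and without it, each with a 95% CI. Give the source-adjusted result for the lean/obese contrast as well.
2. The prior-minus-concurrent UCP1 difference within the obese group, adjusted for age, sex and BMI, with its 95% CI.
3. A statement on interpretation. The BMI version assumes linearity across a gap in the BMI range; the lean/obese version can absorb a real BMI gradient if BMI differs between sources. Disagreement between models therefore does not prove a source effect, and a non-significant source term does not prove that pooling is safe.

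Separately, reconcile the description in Aim 1 of all 155 participants as aged 18-55 with the prior-study ages up to 65 in Section 5.0. A sensitivity analysis limited to ages 18-55 is optional, since the model already adjusts for age.

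The cost is SAP wording and a few models on data already held, with no new participants. The source-adjusted estimates are less precise, by the amounts shown in the working, which is a reason to keep them as sensitivity analyses.
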